6. STUDY PROCEDURES

6.1. Study Measurements and Assessments

6.1.1. Assessment of Safety

Safety assessments will include the following:

- AEs and SAEs, both reported and observed
- Adverse device events (ADE)
- Physical examination
- Vital sign measurements
- Venous blood for clinical laboratory tests will include hematology, coagulation, and blood chemistry.

6.1.2. Exploratory Assessments

While this study is not designed to make conclusions on efficacy, exploratory assessments of efficacy endpoints will be made as previously described.

6.2. Study Phases and Procedures

A Time and Events Schedule is provided in [Appendix 1](#).

6.2.1. Screening Phase (Visit 1; Day -28 through Day 1)

The initial Screening Visit may be conducted up to 28 days prior to Baseline on Day 1. The following procedures/assessments will be performed at Screening:

- Informed consent (must be done prior to any of the following procedures, including asking patients to discontinue prohibited medications)
- Record medical history and patient demographics
- Documentation of prohibited, prior, and current medications with duration of treatment
- Height, weight, and age
- Vital Signs (temperature, blood pressure, respiratory rate, and heart rate) collected after the patient has been upright and rested for at least 5 minutes
- Serum pregnancy test (for all females of child bearing potential)
- Venous blood for clinical laboratory tests
- Venous blood for infectious disease screen (HIV, hepatitis B, and hepatitis C analysis)
- Six-minute walk test (6MWT)
- Pulmonary function testing (FEV1 and FEV1/FVC ratio), with or without bronchodilator
- NYHA Functional Class Assessment
- Assessment of hepatic and renal impairment (See [Appendix 6](#))
- Full physical examination
- Confirm patient meets all eligibility criteria
- Schedule next study visit (Baseline)

The results of all laboratory assessments must be returned and reviewed prior to enrolling the patient for Day 1 procedures.

6.2.2. Baseline – (Visit 2; Day 1)

The description of assessments in this section is intended for patients that are **NOT** enrolled in the PK Sub-Study. Patients who are enrolled in the PK Sub-Study should follow the assessments described in Section [6.2.3](#).

The following assessments are to be completed at Baseline and prior to dose administration:

- Eligibility re-assessment
- Brief physical examination
- Vital signs (temperature, blood pressure, respiratory rate, and heart rate) collected after the patient has been upright and rested for at least 5 minutes
- Weight
- Venous blood for clinical laboratory tests, including NT-proBNP
- Urine pregnancy test (for all females of child bearing potential, Day 1 only)
- 6MWT
- NYHA Functional Class Assessment
- MLWHF questionnaire
- Assessment of PAH Symptoms
- Device training
- Prior medications
- Record time of last dose of inhaled treprostinil
- Administer first dose of LIQ861 (after all other predose assessments)
 - Note that for Tyvaso transition patients, the time of LIQ861 administration should be at least 4 hours after the last dose of Tyvaso

The following assessments are to be completed after dose administration:

- Inhalation Device User Survey
 - The Inhalation Device User Survey should only be administered to Tyvaso Transition patients.
- Concomitant medications
- Treatment-Emergent Adverse Events
- Study Drug Dispensation
- Schedule Next Visit

6.2.3. Baseline – PK Sub-Study (Visit 2; Day 1 & Day 2)

The description of assessments in this section is intended **ONLY** for patients that are enrolled in the PK Sub-Study. Patients that are **NOT** enrolled in the PK Sub-Study should follow the assessments described in Section [6.2.2](#).

Day 1

The following assessments are to be completed at Baseline and prior to Tyvaso administration on Day 1:

- Eligibility re-assessment

- Brief physical examination
- Vital signs (temperature, blood pressure, respiratory rate, and heart rate) collected after the patient has been upright and rested for at least 5 minutes
- Weight
- Venous blood for clinical laboratory tests, including NT-proBNP
- Urine pregnancy test (for all females of child bearing potential, Day 1 only)
- 6MWT
- NYHA Functional Class Assessment
- Assessment of PAH Symptoms
- Prior medications
- Record time of last dose of inhaled treprostinil
- Plasma for baseline PK measurement (must be taken before Tyvaso administration, within 30 minutes of dose administration)
- Final dose of Tyvaso (after all other predose assessments)
 - Note that this must be the first dose of the day. If the subject has taken Tyvaso prior to arrival at the clinic, the PK sub-study should not be conducted or the visit should be rescheduled.

The following assessments are to be completed after Tyvaso administration on Day 1, but before the first dose of LIQ861 is administered:

- Plasma for PK measurements at 5, 10, 15, 20, 25, 30, 45, 60, 90, 120, and 180 minutes and 4 hours after Tyvaso administration. Actual times of blood collection for each timepoint must be recorded.
- Adverse Events
- Concomitant medications
- Venous blood for clinical laboratory tests at 4 hours after Tyvaso administration
- MLWHF questionnaire
- DPI Training

The second treprostinil dose of the day should be the first administration of LIQ861. The following assessments are to be completed after the first dose of LIQ861 is administered:

- Treatment-Emergent Adverse Events
- Concomitant medications
- Inhalation Device User Survey
- Study Drug Dispensation
- Schedule Next Visit

Day 2

The following assessments are to be completed at Baseline and prior to study drug administration on Day 2:

- Treatment-Emergent Adverse Events
- Eligibility re-assessment
- Brief physical examination
- Vital signs (temperature, blood pressure, respiratory rate, and heart rate) collected after the patient has been upright and rested for at least 5 minutes

- Weight
- Venous blood for clinical laboratory tests, including NT-proBNP
- DPI re-training
- Concomitant medications
- Record time of last dose of inhaled treprostinil
- Plasma for baseline PK measurement (must be taken before LIQ861 administration, within 30 minutes of dose administration)
- Administer dose of LIQ861 (after all other predose assessments)
 - Note that this should be the first dose of the day. If the subject has taken LIQ861 prior to arrival at the clinic, then Day 2 of the PK sub-study should be rescheduled.

The following assessments are to be completed after the first study drug administration on Day 2:

- Plasma for PK measurements at 5, 10, 15, 20, 25, 30, 45, 60, 90, 120, and 180 minutes and at 4 hours after study drug administration. Actual times of blood collection for each timepoint must be recorded.
- Concomitant medications
- Venous blood for clinical laboratory tests at 4 hours after study drug administration
- Study Drug Dispensation
- Schedule next visit
- Treatment-Emergent Adverse Events
- Inhalation Device User Survey

6.2.4. Visit 3 (Week 2)

Visit 3 should be scheduled approximately 2 weeks \pm 2 days from the first administration of LIQ861.

The following assessments may be conducted before or after study drug administration at Visit 3:

- NYHA Functional Class Assessment
- Collect unused study drug
- Study drug accountability
- Study drug dispensation
- Schedule next visit
- Assess PAH Symptoms
- Consider dosing adjustments and record any prescribed changes

The following assessments will be conducted prior to study drug administration at Visit 3:

- Vital signs (temperature, blood pressure, respiratory rate, and heart rate) collected after the patient has been upright and rested for at least 5 minutes
- Venous blood for clinical laboratory tests, including NT-proBNP
- DPI re-training
- Concomitant medications
- Treatment-Emergent Adverse Events
- Record time of last dose of inhaled treprostinil
- Administration of study drug

- Note that the time of LIQ861 administration should be at least 4 hours after the last dose of LIQ861.

The following assessments will be conducted after study drug administration at Visit 3:

- 6MWT (within 15 to 60 minutes after administration of LIQ861)
- Concomitant medications
- Treatment-Emergent Adverse Events
- Inhalation Device User Survey
 - The Inhalation Device User Survey should only be administered to Tyvaso Transition patients.

6.2.5. Visits 4 & 5 (Month 1 & Month 2)

Visits 4 and 5 should be scheduled approximately 1 and 2 months \pm 3 days from the first administration of LIQ861, respectively.

The following assessments may be done before or after study drug administration at Visits 4 & 5:

- Brief Physical Examination (Visit 5 only)
- NYHA Functional Class Assessment
- Collect unused study drug
- Study drug accountability
- Study drug dispensation
- Schedule next visit
- Assess PAH Symptoms
- Consider dosing adjustments and record any prescribed changes

The following assessments will be conducted prior to study drug administration at Visits 4 & 5:

- Vital signs (temperature, blood pressure, respiratory rate, and heart rate) collected after the patient has been upright and rested for at least 5 minutes
- Venous blood for clinical laboratory tests, including NT-proBNP
- DPI re-training
- Concomitant medications
- Treatment-Emergent Adverse Events
- Record time of last dose of inhaled treprostinil
- Administration of study drug
 - Note that the time of LIQ861 administration should be at least 4 hours after the last dose of LIQ861

The following assessments will be conducted after study drug administration at Visits 4 & 5:

- 6MWT (within 15 to 60 minutes after administration of LIQ861)
- MLWHF questionnaire (Visit 5 only)
- Concomitant medications
- Treatment-Emergent Adverse Events

6.2.6. Visits 6+ (Month 4)

6.2.6.1. In Clinic at Month 4 and Every 4 Months thereafter until Study Termination Visit

Visit 6 should be scheduled approximately 4 months \pm 7 days from the first administration of LIQ861 and in-clinic follow-up visits should be scheduled every 4 months \pm 7 days thereafter.

The following assessments may be done before or after study drug administration at Visit 6 and all subsequent in clinic follow-up visits:

- Full Physical Examination (at Visit 6 and every 12 months thereafter)
- NYHA Functional Class Assessment
- Collect unused study drug
- Study drug accountability
- Assess PAH Symptoms
- Consider dosing adjustments and record any prescribed changes
- Study drug dispensation
- Schedule next visit
- Schedule telephone follow-up visit for 8 weeks from the current visit to assess AEs, concomitant medications, PAH symptoms, and dose adjustment.

The following assessments will be conducted prior to study drug administration at Visit 6 and all subsequent in clinic follow-up visits:

- Vital signs (temperature, blood pressure, respiratory rate, and heart rate) collected after the patient has been upright and rested for at least 5 minutes (at Visit 6 and every 12 months thereafter)
- Weight (at Visit 6 and every 12 months thereafter)
- Venous blood for clinical laboratory tests
 - NT-proBNP collected at every 4 month visit
 - Hematology and Blood Chemistry collected at Visit 6 and every 12 months thereafter
- DPI re-training
- Concomitant medications
- Treatment-Emergent Adverse Events
- Record time of last dose of inhaled treprostinil
- Administration of study drug
 - Note that the time of LIQ861 administration should be at least 4 hours after the last dose of LIQ861

The following assessments will be conducted after study drug administration at Visit 6 and all subsequent in clinic follow-up visits:

- 6MWT (within 15 to 60 minutes after administration of LIQ861)
- Inhalation Device User Survey (at Visit 6 and every 12 months thereafter)
 - The Inhalation Device User Survey should only be administered to Tyvaso Transition patients.
- MLWHF questionnaire (at Visit 6 and every 12 months thereafter)
- Concomitant medications

- Treatment-Emergent Adverse Events

6.2.6.2. Phone Visits (every 4 months starting at Month 6)

Phone visits (conducted by telephone call) should be scheduled approximately every 4 months ± 3 days starting at Month 6.

The following assessments should be conducted during the Phone Visit:

- Concomitant medications.
- Treatment-Emergent Adverse Events.
- Assess PAH Symptoms.
- Consider dosing adjustments and record any prescribed changes.
- Confirm date of next in clinic follow-up visit.

6.2.6.3. Study Termination Visit

Study termination visits will occur when a patient is discontinued from the study or once the Sponsor has decided to terminate the study.

The following assessments should be conducted during the Study Termination Visit:

- Full Physical Examination
- Weight and height
- Vital Signs (temperature, blood pressure, respiratory rate, and heart rate) collected after the patient has been upright and rested for at least 5 minutes
- Venous blood for clinical laboratory tests, including NT-proBNP
- 6MWT
- NYHA Functional Class Assessment
- Assess PAH Symptoms
- Inhalation Device User Survey
 - The Inhalation Device User Survey should only be administered to Tyvaso Transition patients.
- MLWHF questionnaire
- Record time of last dose of LIQ861
- Treatment-Emergent Adverse Events
- Concomitant medications
- Collect unused study drug
- Study drug accountability

At the Study Termination Visit, Study Drug Dispensation will not be performed and future visits should only be scheduled for follow-up visits in the event of an Early Termination. All remaining supply of Study Drug should be collected and reconciled.

6.2.7. Follow-up for Withdrawn Patients

Follow-up should occur for all patients that are removed from the study (Early Termination) for at least 4 months after receiving the last dose of LIQ861 or until all TEAEs are resolved or stabilized. If the patient was withdrawn from treatment with the study drug for clinical worsening, follow-up visits should be scheduled at the discretion of the investigator for the longer of the following periods:

- at least 4 months from receiving the last dose of LIQ861,
- until, in the opinion of the investigator, the patient is no longer clinically worsened from his or her baseline state, or
- until, in the opinion of the investigator, clinical worsening from baseline state is no longer attributed to treatment with LIQ861.

Follow-up visits may be conducted as telephone calls or in person visits at the Investigational site. At a minimum, follow-up visits should occur at approximately 2 weeks \pm 2 days, and at 2 months and 4 months after receiving the last dose of LIQ861 and include the following assessments:

- Treatment-Emergent Adverse Events
- Concomitant medications

If the patient was withdrawn from treatment with the study drug for clinical worsening, additional assessments for the signs and symptoms that lead to judgement of clinical worsening should be made at all follow-up visits within 4 months of Early Termination or until the signs and symptoms that lead to judgement of clinical worsening are resolved.

6.3. Unscheduled Visits

Unscheduled visits, including telephone calls, may be conducted as needed based on the Investigator's medical judgment. At a minimum, the following safety assessments should be recorded at any unscheduled visits:

- Treatment-Emergent Adverse Events.
- Concomitant medications.
- Dose adjustments.

The following safety assessments may also be recorded at unscheduled visits:

- Physical examination findings.
- Clinical laboratory tests as indicated per Investigator judgment.
- PAH symptoms.

6.4. Pharmacokinetic Assessments

Blood samples for noncompartmental pharmacokinetic analysis will be collected during the PK Sub-Study only as outlined in the Time and Events Schedule in [Appendix 1](#). Approximately 3 mL of whole blood will be collected from an indwelling catheter for each blood draw to yield approximately 1.5 mL of plasma collected for bioanalytical analysis.

Blood samples will be collected in lavender-top tubes with potassium (K₂) EDTA at the following nominal time points defined in the time and events schedule (actual blood sampling times must be recorded in the source and eCRF): predose (within 30 minutes of dose administration) and at 5, 10, 15, 20, 25, 30, 45, 60, 90, 120, and 180 minutes and 4 hours after the start of Tyvaso or LIQ861 inhalation.

Collecting, Processing, and Shipping Pharmacokinetic Samples

Blood samples will be drawn and processed for plasma as described in [Appendix 4](#). The yield of plasma will be subdivided into 2 samples (~0.75 mL each) and frozen at -20°C within 60 minutes of sample collection. One set of these samples will be shipped to the bioanalytical lab for analysis,

as described in [Appendix 4](#), and the other set will be stored at -20°C at the site until disposition instructions are communicated by Liquidia or designee.

6.5. Clinical Laboratory Tests

All routine samples will be analyzed by a licensed clinical laboratory. The clinical laboratory tests are as follows:

- **Hematology/Coagulation:** hemoglobin, hematocrit, white blood cell count with differential, and red blood cell count
- **Blood Chemistry:** Alanine aminotransferase (ALT; SGPT) and Aspartate aminotransferase (AST; SGOT), blood urea nitrogen (BUN), creatinine, alkaline phosphatase, sodium, potassium, magnesium, calcium, chloride, and uric acid.
- **Biomarkers:** NT-proBNP
- **Serum pregnancy test:** β hCG test for females of childbearing potential
- **Urine pregnancy test:** hCG test for females of childbearing potential (Baseline Visit only)

Blood for clinical labs should be collected at predose and at 4 hours post-dose on Day 1 and on Day 2 for patients in the PK sub-study. For all other visits, blood should be collected only at predose.

The Investigator is responsible for determining if out of range laboratory values are clinically significant or not. All clinically significant values will be recorded as AEs in the eCRF and followed until stabilization, resolution, or loss to follow up. Once resolved, the appropriate AE/SAE eCRF page(s) will be updated.

Details on sample collection and processing procedures will be provided in a separate laboratory manual.

6.6. Physical Examinations

A full physical exam (PE) will consist of assessments of the following: skin, ears, nose, throat, head, eyes, lungs/chest, heart, abdomen, musculoskeletal, extremities, neurologic, and lymphatic.

A brief physical exam includes all the body systems of the full PE, except for eyes, musculoskeletal, and neurologic.

All physical exam findings must be assessed as not clinically significant or clinically significant by the Investigator and recorded in the source document and eCRF. Clinically significant changes noted in PE findings should be recorded as an AE.

6.7. Vital Signs

Vital signs will be obtained per site standard of care to include oral temperature ($^{\circ}$ F or $^{\circ}$ C, with units indicated), blood pressure (mmHg), respiratory rate (breaths per minute), and heart rate (beats per minute [bpm]). Blood pressure, respiratory rate, and heart rate will be obtained after the patient has been upright and rested for at least 5 minutes.

6.8. Six-Minute Walk Test (6MWT)

The 6MWT should be performed as described by the guidelines from the American Thoracic Society ([ATS 2002](#)). Required equipment, detailed instructions, and a worksheet for data collection is provided in [Appendix 7](#).

6.9. Assessment Windows

The actual time of the assessments must be recorded. At the Baseline visit, 6MWT should be performed prior to administration of inhaled treprostinil (Tyvaso or LIQ861), and the actual start and end time should be recorded. At all subsequent visits, 6MWT should be performed between 15 and 60 minutes after administration of LIQ861, and the actual start and end time should be recorded.

Collection of PK samples should occur as close to the nominal timepoint as possible. The actual time of PK sample collection will be recorded. All other assessments should be scheduled around the collection of PK samples at their nominal timepoints.

6.10. Patient Questionnaires

For all patients, the MLWHF questionnaire ([Rector and Cohn 1992](#)) will be administered at Baseline (Day 1), Visit 5 (Month 2), Visit 6 (Month 4), and every 12 months thereafter.

For all Tyvaso Transition patients, responses to the Inhalation Device User Survey ([Appendix 5](#)) will be collected at Baseline (Day 1), Visit 3 (Week 2), Visit 6 (Month 4), and every 12 months thereafter.

7. ADVERSE EVENTS

The Investigator is responsible for the detection and documentation of events meeting the definition of an AE or SAE as provided in this protocol. Only Treatment-Emergent AEs (TEAEs) and SAEs (occurring after the first inhalation of LIQ861, or Tyvaso in the PK sub-study, through the appropriate follow-up period) will be recorded in this study.

Definitions and terminology relevant to IND Safety Reports, as referenced in the U.S. Code of Federal Regulations, are addressed below.

7.1. Definition of a Treatment-Emergent Adverse Event

An AE is any untoward medical occurrence associated with the use of a drug in humans, whether or not considered drug related. All AEs that occur after the time of treatment with the investigational product will be considered a Treatment Emergent AE (TEAE).

A TEAE can be any unfavorable and unintended sign (e.g., an abnormal laboratory finding), symptom, or disease temporally associated with the use of a drug, without any judgment about causality.

A TEAE **does** include any:

- Exacerbation of a pre-existing illness.
- Increase in frequency or intensity of a pre-existing episodic event or condition.
- Condition detected or diagnosed after study drug administration even though it may have been present prior to the start of the study.

- Continuous persistent disease or symptoms present at baseline that worsen following the start of the study.
- Events considered by the investigator to be related to study-mandated procedures.
- Abnormal assessments (e.g., change in physical examination), if they represent a clinically relevant finding, that were not present at Baseline or worsened during the course of the study.
- Laboratory test abnormalities, if they represent a clinically relevant finding, symptomatic or not, which were not present at Baseline or worsened during the course of the study.

A TEAE **does not** include a/an:

- Medical or surgical procedure (e.g., surgery, endoscopy, tooth extraction, transfusion); the condition that leads to the procedure is an AE.
- Situations where an untoward medical occurrence has not occurred (e.g., hospitalization for cosmetic elective surgery, social and/or convenience admissions).
- Overdose of either study drug or concurrent medication without any signs or symptoms.
- Hospitalization for elective treatment of a pre-existing condition that did not worsen during the study is not considered an AE.

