3.2. Endpoints

3.2.1. Primary Endpoint

The primary endpoint will be the incidence of Treatment-Emergent Adverse Events (TEAEs) and Serious Adverse Events (SAEs) grouped by MedDRA System Organ Class, dose level, time on drug, and relationship to dose titration.

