Seriousness (not severity) serves as a guide for defining regulatory reporting obligations. An SAE is not necessarily severe (e.g., an overnight hospitalization for a diagnostic procedure must be reported as an SAE even though the occurrence is not medically serious). Similarly, a severe AE is not necessarily serious (e.g., nausea lasting for several hours may be rated as severe but may not be considered serious).

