7.6. Reporting AEs and SAEs

7.6.1. Reporting Adverse Events

AEs occurring from when the patient signs the Informed Consent Form (ICF) until the last study event will be recorded. All AEs and SAEs occurring prior to the first inhalation of LIQ861 will be recorded in the medical history. Also, any sign, symptom, or disease present before the first inhalation of LIQ861 are considered AEs only if they have worsened after the first inhalation of LIQ861.

If the investigator detects an AE in a study patient after the last scheduled follow-up visit and considers the event related to treatment with LIQ861, the investigator should report it to the Sponsor's Medical Monitor.

The investigator should report all AEs on the AE page(s) of the eCRF and source documents, regardless of seriousness, severity, and causality. Whenever possible, an AE will be reported using a diagnostic term (e.g., "common cold" or "upper respiratory infection" rather than "runny nose, cough, mild fever") and should be described with the attributes described in terms of severity (Section 7.3) and relatedness (Section 7.4).

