9.1.7. Case Report Forms

For each patient who receives study drug, an eCRF must be completed and signed by the principal Investigator or sub-Investigator within a reasonable time period after data collection. This also applies to records for those patients who fail to complete the study. If a patient withdraws from the study, the reason must be noted on the eCRF. If a patient is withdrawn from the study because

of a treatment-limiting adverse event, thorough efforts should be made to clearly document the outcome.

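### Protocol 7.1 and 7.6.1 give opposite rules for an unworsened condition first found on LIQ861, so TEAE and SAE counts can depend on which section a site follows

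*Protocol*

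**What the plan says.** Protocol 3.2.1 ties the main result to these definitions: "The primary endpoint will be the incidence of Treatment-Emergent Adverse Events (TEAEs) and Serious Adverse Events (SAEs) grouped by MedDRA System Organ Class", and further by dose level, time on drug and titration.

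- **Protocol 7.1** defines a TEAE as an AE arising after treatment with the investigational product. Among the inclusions is a "Condition detected or diagnosed after study drug administration even though it may have been present prior to the start of the study". Two other inclusions, on abnormal assessments and on laboratory abnormalities, require that the finding was absent at Baseline or became worse. The list also includes "Events considered by the investigator to be related to study-mandated procedures". The exclusions cover procedures (the condition behind the procedure is the AE), "Situations where an untoward medical occurrence has not occurred", and admission for elective treatment of an unworsened pre-existing condition.
- **Protocol 7.6.1** says that signs, symptoms or diseases "present before the first inhalation of LIQ861 are considered AEs only if they have worsened after the first inhalation of LIQ861". It records AEs from consent onward but places those before the first LIQ861 inhalation, SAEs included, in medical history.
- **Protocol 7.1.4** makes seriousness a property of a TEAE or suspected adverse reaction. It then gives as an example that "an overnight hospitalization for a diagnostic procedure must be reported as an SAE even though the occurrence is not medically serious".
- **Protocol 7 (opening paragraph)** and **Appendix 1, main schedule, footnote n** limit collection to treatment-emergent events. The opening paragraph starts the clock at Tyvaso for the PK sub-study.
- **Protocol 9.1.7**: "For each patient who receives study drug, an eCRF must be completed".
- **SAP 8.1** treats an AE as treatment-emergent unless it clearly occurred before the first dose, and tabulates TEAEs only. **SAP 5.2** gives a Safety Population of 121 (55 Transition, 66 Add-On).

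**The concern.** The trial has no formal hypothesis test (Protocol 8.4), so the event counts are themselves the result. If two sections of the same protocol classify the same event differently, sites that follow different sections will enter different data. Protocol 7.1 would have a site enter a pre-existing condition that first comes to light on drug, and 7.6.1 would have it left off the AE page. The difference then shows up in the System Organ Class and Preferred Term tables, and in the SAE counts if the event is serious. The study allows up to 50 sites, so uniform practice cannot be assumed.

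**Working it through.** The plan states no figure to reproduce on this point. The check is a comparison of rules, followed by simple proportions for scale.

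**Step 1. Condition first found on drug.** Take a condition that existed before the first inhalation, did not worsen, and was first diagnosed after dosing.

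- Under 7.1 it is a TEAE, because detection after dosing is enough.
- Under 7.6.1 it is not an AE, because it was present before dosing and did not worsen.
- Other text does not settle it. Protocol 7.6.5 has relevant abnormal findings detected after the first inhalation assessed against AE criteria, which leans towards 7.1. The two bullets in 7.1 that require absence at Baseline or worsening lean towards 7.6.1.
- SAP 8.1 defaults to treatment-emergent, but it acts only on events entered as AEs. A site that follows 7.6.1 enters nothing, so there is nothing for the default to act on.

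**Step 2. Overnight diagnostic admission.**

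- If a new or worsened condition led to the admission, 7.1 makes that condition the AE, and 7.1.4 makes it serious because of the stay. The texts agree.
- If there is no new or worsened condition, for example a planned work-up, 7.1 finds no AE and the lead sentence of 7.1.4 then has nothing to call serious. The example in 7.1.4 nevertheless requires an SAE report. The elective exclusion covers treatment and does not mention diagnosis, so it gives no relief. The ambiguity is confined to this case.

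**Step 3. Events related to screening procedures.**

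- The bullet on study-mandated procedures has no time limit of its own, but it sits under a definition restricted to events after treatment. A screening event is therefore not a TEAE under 7.1.
- SAP 8.1 keeps clearly pre-dose events out of the tables, and the Safety Population contains dosed subjects only. The primary endpoint is unaffected.
- What remains is a conflict about recording. Protocol 7 and footnote n collect only treatment-emergent events, while 7.6.1 records from consent and sends pre-dose SAEs to medical history. Section 9.1.7 requires an eCRF only for dosed patients.
- The PK sub-study has a related mismatch: Protocol 7 records events after Tyvaso, but 7.6.1 sends anything before the first LIQ861 inhalation to medical history.

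**Step 4. Scale.** If k subjects have a given row of a table decided only by the disputed rule, that incidence moves by k/N.

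| Group | N | k = 1 | k = 6 |
|---|---|---|---|
| Overall | 121 | 1/121 = 0.8 points | 6/121 = 5.0 points |
| Transition | 55 | 1/55 = 1.8 points | 6/55 = 10.9 points |
| Add-On | 66 | 1/66 = 1.5 points | 6/66 = 9.1 points |

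The documents do not give k. The range 1 to 6 is an assumption made only to show scale, and the group rows suppose that all k subjects fall in that group.

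For the recording conflict in Step 3, SAP 5.1 and 5.2 give 146 screened and 121 dosed: 146 − 121 = 25, and 25/146 = 17.1%. This is an upper bound on the subjects exposed to the eCRF gap. It does not count events, or subjects known to have done the walk test or spirometry.

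**The case against.** The best reply on Step 1 is that the 7.6.1 sentence directly follows the medical-history rule, so it can be read as covering only conditions already known. Protocol 7.6.5 makes a similar split between findings detected after dosing and findings present earlier that worsen, and SAP 8.1 leans the same way. That reading is workable and is close to the fix proposed below. But it is not what 7.6.1 says: the sentence turns on presence, with no mention of prior knowledge. A site that reads it literally would be following the protocol.

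On Step 2, the overnight stay is a parenthetical example separating seriousness from severity. Read in order, an occurrence that is not an AE never reaches the seriousness test. This stands in part: no sentence directly says the opposite of the example, so it is an ambiguity and not a flat contradiction. The mandatory wording still invites SAE reports for planned work-ups.

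A reader might infer that screening-procedure events also shift the primary endpoint, or that serious screening events need no record at all. The documents support neither. The first fails for the reasons in Step 3. On the second, 7.6.1 does call for a medical-history entry, and the 24-hour rule in 7.6.2 states no dosing condition. The doubt is narrower: 7.1.4 ties seriousness to a TEAE or suspected adverse reaction, so it is unclear whether 7.6.2 reaches a screening event, and no eCRF is required to carry the entry for a patient never dosed.

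It is also fair to say that rewording the protocol cannot by itself reclassify data already collected. SAP 3.3 reports that 121 subjects were enrolled, and SAP 2 says that data through Month 2 have been reported.

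**Conclusion.** The contradiction between 7.1 and 7.6.1 is real and feeds the primary endpoint, and the SAP cannot repair it. The overnight-admission wording is a secondary ambiguity, limited to stays with no new or worsened condition. The screening and Tyvaso items are recording conflicts to be reconciled separately. The screening conflict does not affect the primary endpoint.

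The size is at most 0.8 points per reclassified subject overall, 1.8 in Transition and 1.5 in Add-On. The number of such subjects is unknown. The effect falls mainly on System Organ Class and Preferred Term rows and on SAE counts, because the any-TEAE row does not change for a subject who has another TEAE. A reader might go further and conclude that the primary endpoint as a whole turns on which paragraph a site follows. That is too broad, since most events are classified alike under either section. The conclusion assumes that at least some sites applied 7.6.1 as written, which the documents cannot confirm.

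**What to change.** 1. **Main change.** Amend 7.6.1 so that a condition first diagnosed after dosing is a TEAE unless source records document it, unworsened, before the first dose. This agrees with the detection rule in 7.1 and with the default in SAP 8.1.
2. **Secondary change.** State in 7.1.4 that an overnight diagnostic admission is an SAE only when an AE led to it.
3. **Separate change.** Reconcile the opening of Protocol 7, Appendix 1 footnote n, 7.6.1 and 9.1.7, so that SAEs related to protocol-mandated screening procedures are reported to the sponsor and listed outside the TEAE tables. Use the same edit to reconcile Protocol 7 and 7.6.1 on PK sub-study events after Tyvaso and before LIQ861.
4. **Data already collected.** Document the reconciled rule and query affected records before database lock, which is the limit SAP 2 sets for SAP amendments. Candidates are medical-history entries with a diagnosis date after the first dose, and SAE reports whose only ground is an overnight diagnostic stay. Report any change from the Month 2 counts in the final study report.

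The cost is a protocol clarification with a site memo, some queries and one extra listing.
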